5. SURVEILLANCE MONITORING PLAN

This is a single-arm, open-label phase II clinical trial evaluating delayed start olaparib maintenance therapy, based on a rise in CA125, for patients with epithelial ovarian cancer who have had a partial or complete response to platinum-based treatment. Patients will be enrolled within 8 weeks of completing platinum-based therapy for recurrent disease. At the time of enrollment, patients will be monitored with CA125 levels every 28 days.

At the first evidence of a two-fold rise in CA125 from baseline, patients will undergo a CT scan to evaluate for any visible lesions, including new lesions for those with CR and new, persistent or progressive lesions for those with PR to most recent therapy, and then will be started on olaparib therapy. In the setting of new or progressive lesions, patients will be followed per protocol. Patients may undergo CT imaging prior to rise in CA-125 at the discretion of the treating physician for patient symptoms. Eighty-one patients will be enrolled through UPMC medical and gynecologic oncology offices.

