- H. Financial toxicity will be measured through a) monetary measure using the Modified Collection of Indirect and Nonmedical Direct Costs (COIN) (See Appendix I), b) objective measure of financial burden assessed using Barrera et al.'s Economic Hardship questionnaire (See Appendix J), and c) subjective measure of financial distress will be gauged using the Comprehensive Score for Financial Toxicity (COST Measure) (See Appendix K).
- I. Pregnancy test for women of childbearing potential (WOCBP) must be done within 24 hours prior to initiation of olaparib.
- J. Tissue collection is not mandatory. If permission granted, tissue prior to initiation on olaparib will be obtained from archival stores. If patient undergoes biopsy at the time of progression as part of standard of care, tissue will be collected after routine processing.
- K. A mandatory trough plasma sample will be obtained only once at approximately 28 days after initiation of treatment (See **Appendix L**).
- L. BRCA testing required (Results not needed for registration
- M. Chart review or office visit every 3 months for 18 months from time of enrollment

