14. STATISTICAL CONSIDERATIONS

14.1 Study Design/Endpoints

Primary endpoint is defined as the time to next therapy from completion of platinum-based therapy for treatment of recurrence until initiation of post-olaparib treatment. Based on Ledermann et al,²⁹ the expected median time to progression on olaparib following platinum response is 8.4 months for a cohort with 22% *BRCA* mutation prevalence.

Secondary endpoints

Progression-free survival is defined as the time from enrollment until detected recurrence or progression of disease, via RECISTv1.1, or death from any cause.

- Overall survival as defined as the time from enrollment to death from any cause.
- Toxicity rates defined by the National Cancer Institute's Common Terminology Criteria for Adverse Events (CTCAE) v5.0.
- Response rate as defined by RECIST or CA-125 and stratified by *BRCA* mutation status.
- Patient-reported adverse events using the NCI Patient Reported Outcomes-Common Terminology Criteria for Adverse Events (PRO-CTCAE) (See Appendix
- Health-related quality of life measured via The Functional Assessment of Cancer Therapy + Ovarian-specific scale (FACT-O)
- Physical function assessed through the PROMIS Physical Function-20a assesses self-reported performance of physical activities
- Worry and distress measured via Assessment of Survivor Concerns (ASC) Worry Subscale and Impact of Event Scale (IES-R)
- Financial toxicity measured through

a) monetary measure using the Modified Collection of Indirect and Nonmedical Direct Costs (COIN),

b) objective measure of financial burden assessed using Barrera et al.'s Economic Hardship questionnaire⁵¹, and

c) subjective measure of financial distress will be gauged using the Comprehensive Score for Financial Toxicity (COST Measure).

• Exposure measured through quantitating olaparib by LC-MS/MS in a trough sample.

PLANNED ENROLLMENT REPORT

Page 37 of

Racial Categories	Ethnic Cate	Total		
	Not Hispanic or Latino	Hispanic or Latino		
	Female	Female		
American Indian/ Alaska Native	0	0	0	

	Ethnic Cat		
Racial Categories	Not Hispanic or Latino	Hispanic or Latino	Total
	Female	Female	
Asian	3	0	3
Native Hawaiian or Other Pacific Islander	0	0	0
Black or African American	7	0	7
White	65	0	65
More Than One Race	0	0	0
Total	75	0	75

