13.2 SAMPLE SIZE/ACCRUAL RATE

Study 19 is the only PARP inhibitor maintenance trial in the platinum sensitive recurrent setting to report both PFS and OS data. Median progression-free survival was 8.4 months in the olaparib group versus 4.8 months in the placebo group (hazard ratio for progression or death, 0.35; 95% confidence interval [CI], 0.25 to 0.49; P<0.001). The secondary end point of time to progression according to the RECIST guidelines or CA-125 level, whichever showed earlier progression, was also significantly longer in the olaparib group than in the placebo group (median, 8.3 months vs. 3.7 months; hazard ratio for progression, 0.35; 95% CI, 0.25 to 0.47; P<0.001). There was no statistically significant OS advantage noted for those treated with olaparib; for the entire population median OS was 29.8-months-[95%-CI-26·9–35·7]-in the olaparib arm vs 27.8 months-[24·9–33·7] in the placebo arm. For those patients evaluable for response (n=61), there were 16 (26.2%) either PR or CR by RECIST and 1 (1.6%) by CA125²⁹.

Using the reported data from Study 19, we will assess whether delaying olaparib until biochemical relapse will increase the median time to next treatment by \sim 3 months (from 8 to 11 months). We assume 3-4 patients can be accrued/month and that the *BRCA* mutation

prevalence will be ~20% and thereby be comparable to the historical control group. With 2 years of accrual and 18 months of additional follow up, we will require 75 eligible patients. This will allow 90% power for a level 0.10 one-sided one sample exponential test to detect an improvement in median time to next treatment from 8 to 11 months. Due to the possibility of lost to long-term follow-up, we plan to accrue an additional 10% of the targeted accrual. Therefore, the sample size for this study will be approximately 83 patients in order to successfully accrue 75 evaluable patients.

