13.3 DATA ANALYSIS

13.3.1 Analysis Sets

Evaluable patients: patients who meet all of the protocol inclusion/exclusion criteria and begin treatment with the protocol regimen.

Safety set: data from all evaluable patients who receive initial treatment of the study treatment will be used in the analysis of safety.

Efficacy set: data from all evaluable patients who receive initial treatment of the study treatment will be used in the analysis of efficacy endpoints.

Exploratory set: the data from all study-eligible patients (i.e. those meeting all of the protocol inclusion/exclusion criteria) who begin the study treatment and have tissue samples taken will be used in the analyses to address the correlative biomarker aims.

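### The 90% power is sound for 75 evaluable patients, but the number to enrol, one follow-up footnote and the open choice of primary test do not carry its inputs through the plan

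*Combined protocol and SAP*

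**What the plan says.** **Power.** Section 13.2 (Sample Size/Accrual Rate) says "With 2 years of accrual and 18 months of additional follow up, we will require 75 eligible patients" and "This will allow 90% power for a level 0.10 one-sided one sample exponential test", for a median time to next treatment of 8 months against 11.

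**Number to enrol.** The same section adds a margin: "Due to the possibility of lost to long-term follow-up, we plan to accrue an additional 10% of the targeted accrual". It concludes that "the sample size for this study will be approximately 83 patients in order to successfully accrue 75 evaluable patients". Section 5 says "Eighty-one patients will be enrolled through UPMC medical and gynecologic oncology offices". The synopsis gives 75 as the number of subjects, and the table headed "PLANNED ENROLLMENT REPORT" (after Section 14.1) totals 75. Section 13.3.1 defines evaluable patients as "patients who meet all of the protocol inclusion/exclusion criteria and begin treatment with the protocol regimen".

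**Follow-up.** Footnote M in Section 11, attached to the survival follow-up row, reads "Chart review or office visit every 3 months for 18 months from time of enrollment". Section 6.4 follows patients to the next therapy after olaparib and makes 18 months from enrolment a minimum. Section 6.6 keeps patients on study until that therapy starts. Sections 13.2 and 13.3.4 count 18 months from the last accrual, and the synopsis gives a 42-month study (24 + 18).

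**Primary test.** Section 13.3.4 specifies a one-tailed exponential test at 0.10. If the data are not exponential, it allows either another parametric test or a one-sample log-rank test. It gives no criterion for leaving the exponential test, no rule for choosing between the two fallbacks, no named parametric model and no null for either.

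**The concern.** The power statement needs 75 evaluable patients, follow-up to a common cut-off 18 months after the last accrual, and one test with a known error rate.

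- A team working from the synopsis or the enrolment table could close accrual at 75 and have no margin for loss. The 10% margin is justified by loss to long-term follow-up, yet evaluability depends on starting treatment. In this design olaparib starts only after CA-125 doubles, so never starting is a separate way to leave the 75. The plan does not say which loss the extra patients cover.
- A coordinator working from the calendar could stop 3-monthly chart review at month 18.
- A statistician reaching 13.3.4 could choose the test with the data in hand. A constant hazard of next treatment is doubtful when a surveillance period is followed by an olaparib period. The assumption may well be questioned at analysis, with no rule in place.

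**Working it through.** **Inputs from 13.2:** one-sided alpha 0.10 and power 0.90 (z = 1.2816 for each), medians 8 and 11 months, uniform accrual over 24 months plus 18, N = 75. Effect r = ln(11/8) = 0.3185.

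**Step 1: the plan's own figure.**

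- Events needed = [(1.2816 + 1.2816)/0.3185]² = 64.8.
- Probability of an observed event, with λ = ln 2/median: 1 − [exp(−18λ) − exp(−42λ)]/(24λ). This is 0.912 at median 8 and 0.834 at median 11.
- Expected events at median 11: 75 × 0.834 = 62.6.
- Power with the alternative variance only: Φ(0.3185 × √62.6 − 1.2816) = 0.892.
- Power with null and alternative variances: Φ[(0.3185 − 1.2816/√(75 × 0.912)) × √62.6] = 0.902.
- Simulation gives 0.89 for the exponential test.

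The stated 90% therefore reproduces.

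**Step 2: number to enrol.** 75 × 1.10 = 82.5, so 83 follows from 13.2. Dividing instead, 75/0.90 = 83.3. Neither route gives 81 (81/75 = 1.08). Power under a 10% loss, using the alternative-variance formula:

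| Enrolled | Lost patients removed | Lost patients censored |
|---|---|---|
| 83 | 74.7 left, 62.3 events, 0.891 | 65.2 events, 0.901 |
| 81 | 72.9 left, 60.8 events, 0.885 | 63.6 events, 0.896 |
| 75 | 67 left, 55.9 events, 0.864 | 58.9 events, 0.878 |

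The censored column assumes exponential loss reaching 10% by 18 months. On the 13.3.1 definition, 83 enrolled yields 75 evaluable only if at most 8 (8/83 = 9.6%) fail to start treatment.

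**Step 3: footnote M, if it capped the primary endpoint.** The primary clock starts at completion of platinum therapy, and enrolment may follow by up to 8 weeks. Eighteen months from enrolment is therefore 18 to about 20 months on that clock. With 75 patients and no loss:

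- 18 months: 50.9 events, power 0.839 (0.861 with both variances, 0.854 simulated).
- 20 months: 53.7 events, power 0.854 (0.873 with both variances, 0.866 simulated).

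**Step 4: the test when the hazard is not constant.** Simulation with 75 patients, 24 + 18 months and no loss. Power is at median 11 and size at median 8. The Weibull shapes are assumptions; the documents give none.

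| Shape | Exponential test, power/size | Log-rank, null of the true shape with median 8, power/size |
|---|---|---|
| 0.93 | 93%/18% | 85%/9% |
| 1 | 89%/9% | 89%/9% |
| 1.3 | 63%/0.1% | 98%/9% |

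A one-sample log-rank test against an exponential null with median 8 agrees with the exponential test to within 0.001 in these settings. What protects the error rate is the shape of the null curve, not the change of test.

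**The case against.** The strongest reply is that Section 13.2 is coherent by itself: 75 is the evaluable target, about 83 is the number enrolled to reach it, and the power depends on the former. That stands. A reader might infer from the three enrolment figures that the power calculation is wrong or that the 75 evaluable is contradicted, and the documents support neither. The fall to 86–88% also requires accrual actually to stop at 75 and 10% then to be lost, whereas 13.2 plans to over-accrue to prevent this.

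On follow-up, a reader might infer that footnote M ends observation of the primary endpoint early. The documents do not support that. The footnote sits on the survival row, and it can be read as scheduling the minimum that 6.4 sets. Sections 6.4 and 6.6 follow patients to next therapy, and patients in surveillance or on olaparib keep visits every four weeks, at which a later next therapy could still be recorded. The 84–87% is thus the most the footnote could do.

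On the test, the plan recognises that times may not be exponential and names a log-rank fallback. Against a null curve of the right shape, that fallback holds its size and performs well. It would be wrong to infer that the fallback is useless. It is incomplete, because no null is stated. The open choice of test is an underspecified analysis; it is not an error in the power inputs.

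**Conclusion.** The point holds in limited form and should be fixed before data are seen. It does not invalidate the design.

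- **Enrolment:** a genuine inconsistency with a small effect. Power is about 86–88% if 75 are enrolled and 10% are lost, and 88–90% with 81, against 89–90% with 83. These figures assume exponential times.
- **Footnote M:** out of line with 6.4, 13.2 and 13.3.4. It matters for power only under a reading that the other sections contradict, and then takes it to about 84–87%.
- **Primary test:** the most consequential part. The 10% level and 90% power apply to the median only if the hazard is constant. At assumed shapes of 0.93 and 1.3 the exponential test has size 18% and power 63% respectively. The true shape is unknown, so these show sensitivity and are not predictions. The missing selection rule and missing null do not depend on those assumptions: a test chosen after seeing the data has no defined error rate.

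**What to change.** 1. **Enrolment.** State about 83 enrolled, to obtain 75 evaluable, in the synopsis, Section 5, the enrolment table and 13.2. Scaled by its own proportions, the table becomes 72 White, 8 Black or African American and 3 Asian (65, 7 and 3, each × 83/75). Say in 13.2 whether the extra 8 cover loss to follow-up, patients who never start olaparib, or both. If 75 enrolled is what is meant, delete 83 and restate power as about 86–88%.
2. **Footnote M.** Reword it as every 3 months for at least 18 months from enrolment and until the common cut-off 18 months after the last accrual, continuing for survival after next therapy has started. The last clause matters, because follow-up that ended at next therapy would cut off overall survival.
3. **Primary test.** In 13.3.4, before data are seen, name one primary test and its null, remove the open alternative, and restate power in 13.2 for that test. One choice is the plan's own one-sample log-rank test against a pre-stated null curve with median 8 months. If that curve is exponential, it is in effect the present test, with the same sensitivity to a changing hazard. With another curve it keeps size near 9% only if the shape is right, so the curve needs a stated justification.

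Items 1 and 2 cost wording changes and some extra chart reviews. Item 3 costs a justified null curve and one recalculation; whether the sample size changes depends on the test chosen.

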13.3 DATA ANALYSIS

13.3.1 Analysis Sets

Evaluable patients: patients who meet all of the protocol inclusion/exclusion criteria and begin treatment with the protocol regimen.

Safety set: data from all evaluable patients who receive initial treatment of the study treatment will be used in the analysis of safety.

Efficacy set: data from all evaluable patients who receive initial treatment of the study treatment will be used in the analysis of efficacy endpoints.

Exploratory set: the data from all study-eligible patients (i.e. those meeting all of the protocol inclusion/exclusion criteria) who begin the study treatment and have tissue samples taken will be used in the analyses to address the correlative biomarker aims.

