4. SUBJECT SCREENING AND REGISTRATION PROCEDURES

Subjects will be identified in the outpatient clinic. After informed consent is obtained, all patients satisfying the inclusion/exclusion criteria must have eligibility confirmed by the Clinical Trials

Office. The patient will not be considered registered and enrolled in the study until all information is confirmed by the Clinical Trials Office of Research Staff. To enroll a patient, contact the Gyn/Onc Research group Monday through Friday, 8:00AM-4:00PM.

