7. DOSING DELAYS/DOSE MODIFICATIONS

Any patient who receives treatment on this protocol will be evaluable for toxicity. Each patient will be assessed for the development of toxicity. Toxicity will be assessed according to the NCI Common Terminology Criteria for Adverse Events (CTCAE), version 5, and the NCI Patient Reported Outcomes-Common Terminology Criteria for Adverse Events (PRO-CTCAE).

Toxicity/Grade	Dose Adjustment and Management
·	Recommendations
Anemia (Hemoglobin)	
Grade 1 (\geq 10.0 – LLN g/dL)	No dose adjustment required.
Grade 2 (≥8.0 – <10.0 g/dL)	No dose adjustment required.
Grade 3 (<8.0 g/dL)	Dose interruption until recovery to grade ≤ 1 .
	Monitor hemoglobin weekly until recovery.
	If resolves to grade ≤ 1 within 28 days, resume at reduced dose 250 mg PO BID.
	Dose may be reduced to 200 mg PO BID if recurs at
	reduced dose, but if recurs for a third time, treatment
	should be discontinued.
Grade 4 Life-threatening	Dose interruption until recovery to grade ≤ 1 .
consequences; urgent intervention	Monitor hemoglobin weekly until recovery.
indicated	If resolves to grade ≤ 1 within 28 days, resume at reduced dose 250 mg PO BID.
	Dose may be reduced to 200 mg PO BID if recurs at
	reduced dose, but if recurs for a third time, treatment
	should be discontinued.
Thrombocytopenia	
Grade 1 (≥75 x 10 ⁹ /L)	No dose adjustment required.
Grade 2 ($\geq 50 \times 10^9/L - <75 \times 10^9/L$)	Dose interruption until recovery to grade ≤ 1 .
	Monitor platelets weekly until recovery.
	If resolves to grade ≤ 1 within 28 days, resume at reduced dose 250 mg PO BID.

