12.1.1. Definitions

Evaluable for toxicity. All patients will be evaluable for toxicity from the time of their first treatment with olaparib.

Evaluable for objective response by RECIST. Patients who have received at least 1 cycle of therapy and have had their disease re-evaluated with a 3-month post treatment CT will be considered evaluable for response. These patients will have their response classified according to the definitions stated below. (Note: Patients who exhibit objective disease progression prior to the end of cycle 1 will also be considered evaluable.)

Evaluable for objective response by CA-125. Patients who have received at least 1 cycle of therapy, have a CA-125 before treatment below the upper limit of the normal (for values above this limit, any increase in a second sample has to be <15% increase) and have had their disease re-evaluated with monthly CA125, will be considered evaluable for response. These patients will have their response classified according to the definitions stated below. (Note: Patients who exhibit objective disease progression prior to the end of cycle 1 will also be considered evaluable.)

Evaluable Non-Target Disease Response. Patients who have lesions present at baseline that are evaluable but do not meet the definitions of measurable disease, have received at least one cycle of therapy, and have had their disease re-evaluated, will be considered evaluable for non-target disease. The response assessment is based on the presence, absence, or unequivocal progression of the lesions.

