13.3.3 Analysis of Safety Endpoints

The NCI common terminology criteria for adverse events (CTCAE 5.0) will be used to evaluate toxicity; we will consider a toxicity to be an adverse event that is possibly, probably or definitely related to treatment. The maximum grade of toxicity for each category of interest will be recorded for each patient and the summary results will be tabulated by category and grade. Statistics on the number of cycles received by patients and any dose reductions will also be tabulated.

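### Section 13.3.1 limits the safety set to treated patients who meet every eligibility criterion, in conflict with Sections 7 and 12.1.1

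*Combined protocol and SAP*

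**What the plan says.** The analysis sets are nested. Section 13.3.1 first defines a base group: "Evaluable patients: patients who meet all of the protocol inclusion/exclusion criteria and begin treatment with the protocol regimen". The safety set is then taken from it: "Safety set: data from all evaluable patients who receive initial treatment of the study treatment will be used in the analysis of safety". The efficacy set has the same membership rule: "Efficacy set: data from all evaluable patients who receive initial treatment of the study treatment will be used in the analysis of efficacy endpoints".

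Two other sections define who counts for toxicity. Section 7 says: "Any patient who receives treatment on this protocol will be evaluable for toxicity". Section 12.1.1 says: "All patients will be evaluable for toxicity from the time of their first treatment with olaparib". Neither mentions eligibility.

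Section 13.3.3 describes the safety analysis: "The maximum grade of toxicity for each category of interest will be recorded for each patient and the summary results will be tabulated by category". The tables are also broken down by grade, and cycles received and dose reductions are tabulated too. The section does not say which patients enter these tables, so the population falls back on Section 13.3.1.

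**The concern.** Toxicity is a stated secondary endpoint (Section 1.2.3), and the plan gives it two different denominators. An analyst cannot follow both Section 13.3.1 and Sections 7 and 12.1.1 once a treated patient turns out to have breached a criterion.

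For safety, what matters is exposure to the drug. An eligibility filter may be arguable for efficacy, but it serves no evident purpose in a toxicity table. Several criteria in Sections 3.1 and 3.2 are safety limits (marrow, renal and hepatic function, uncontrolled illness). A patient who breached one of these and was still treated may be at higher risk of toxicity, and she is the patient the rule removes. If the conflict is still open at analysis, the denominator could also be chosen after the toxicities are known.

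**Working it through.** The point rests on text, and the plan states no figure to reproduce. The definitions side by side:

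| Place | Must have taken olaparib? | Must meet all criteria? |
|---|---|---|
| Section 7 | Yes | No |
| Section 12.1.1 | Yes | No |
| Section 13.3.1, safety set | Yes | Yes, through the evaluable group |
| Section 13.3.3 | Not stated | Not stated |

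The rules agree for every eligible treated patient. They differ only for a patient who was treated and is later judged ineligible.

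**Size of the difference.** Let N be the number treated, k the number of these who are ineligible, j the number of ineligible patients with the event, and e the number of eligible patients with it.

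- Rate under Sections 7 and 12.1.1: (e + j)/N.
- Rate under Section 13.3.1: e/(N − k).
- Difference: (k/N) × [j/k − e/(N − k)].

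The shift is therefore the ineligible fraction times the gap in event rate between ineligible and eligible patients. It lowers the reported rate only if ineligible patients have more events than the rest.

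**Inputs.** The documents give neither N nor k. The accrual figures are 75 (synopsis), 81 (Section 5) and about 83 (Section 13.2, sample size), but olaparib starts only after CA125 doubles, so the number treated may be smaller. I assume N = 80, k = 3 and e = 17 for grade 3 or higher toxicity.

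| Ineligible patients with event (j of 3) | Sections 7 and 12.1.1 | Section 13.3.1 | Effect of the 13.3.1 rule |
|---|---|---|---|
| 3 | 20/80 = 25.0% | 17/77 = 22.1% | 2.9 points lower |
| 1 | 18/80 = 22.5% | 17/77 = 22.1% | 0.4 points lower |
| 0 | 17/80 = 21.3% | 17/77 = 22.1% | 0.8 points higher |

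Check of the first row by the formula: (3/80) × (3/3 − 17/77) = 0.0375 × 0.779 = 0.029.

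**Range over k**, starting from 20/80 = 25.0% and assuming that every ineligible patient had the event:

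- k = 1: 19/79 = 24.1%
- k = 3: 17/77 = 22.1%
- k = 5: 15/75 = 20.0%

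These are extremes. For scale, the binomial standard error of 25% with 80 patients is √(0.25 × 0.75/80) = 4.8 points. A smaller treated group would make each exclusion count for more.

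**The case against.** The strongest reply is that the rule will seldom bite. Section 3 has the principal investigator or a designee review the baseline results before enrolment, and Section 4 adds that "all patients satisfying the inclusion/exclusion criteria must have eligibility confirmed by the Clinical Trials" Office. Toxicity is also descriptive: Section 13.3.3 sets no test or boundary on it. All of this stands and limits the weight of the point. It does not remove the conflict, because ineligibility can still be found later. The eligibility lists also differ as they stand: the synopsis gives a separate bilirubin allowance for Gilbert syndrome that Section 3.1.7 does not show, so whether a patient meets all criteria can depend on which list is read. Those passages need to be reconciled.

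Three stronger readings are tempting, and the documents do not support them.

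- **A reader might infer that a serious event in an ineligible patient would go unreported.** Section 8.3 requires expedited reporting of deaths and serious events, Section 8.4 routine reporting of all adverse events, and Section 8.5 reporting of secondary malignancies, naming AML and MDS. Section 13.2.1 provides monthly review of serious events. None of this is confined to evaluable patients. Only the summary tables lose the event.
- **A reader might infer that the bias must be downwards.** Many criteria are not safety limits: the definition of platinum sensitivity, prior response, BRCA testing, the 8-week window, history of non-compliance. In addition, Section 11 places baseline tests before the start of the trial, while olaparib starts only when CA125 later doubles. A laboratory breach at enrolment may therefore say little about the patient's state at first dose.
- **A reader might take 25.0% against 22.1% as the expected effect.** It requires all 3 ineligible patients to have the event, against about 22% of the others.

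**Conclusion.** The conflict is real and follows directly from the nested definitions. Section 13.3.1 states a rule that, if followed, drops treated but ineligible patients from the summary toxicity and exposure tables, while Sections 7 and 12.1.1 keep them in.

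The practical effect is probably small. Under the assumed 80 treated and 3 ineligible, it runs from about 3 points too low in the worst case to slightly under 1 point too high if no ineligible patient has the event. Both counts are assumptions, and the direction depends on which criteria are breached. The primary endpoint, sample size and power are not affected. The wording should be corrected because the stated rule is wrong for a safety analysis and contradicts the protocol's own text elsewhere.

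**What to change.** In Section 13.3.1, replace the definition with: *Safety set: all patients who take at least one dose of olaparib, regardless of eligibility.* Detach it from the evaluable group so that it matches Sections 7 and 12.1.1. State in Section 13.3.3 that the toxicity, cycle and dose-reduction tables use this set, and flag ineligible patients in them so that a reader can see their contribution.

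The cost is a sentence or two of wording. No new data are needed, because adverse events are already collected for all treated patients, and the efficacy set can stay as it is. The change should be made before the safety data are analysed.
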